**ABBREVIATIONS AND DEFINITIONS OF TERMS**

ALL	Acute lymphoblastic leukemia
CCSS	Childhood Cancer Survivor Study
CHOP	Children's Hospital of Philadelphia
COG	Children's Oncology Group
CRB	Central Review Board
CT	Computed Tomography
DFCI	Dana-Farber Cancer Institute
HCT	Allogeneic Hematopoietic Cell Transplantation
HMH	Household Material Hardship
IgG	Immunoglobulin G
IRB	Institutional Review Board
IPD	Invasive Pneumococcal Disease
MRI	Magnetic Resonance Imaging
NCCN	National Comprehensive Cancer Network
PMBCs	Peripheral blood mononuclear cells
REDCap TM	Research Electronic Data Capture
Tfh	T follicular helper cells

---

## ABSTRACT

### Context:

Advancements in therapy have led to significant improvement in outcomes for children diagnosed with acute lymphoblastic leukemia (ALL), with overall survival rates now exceeding 90%. Although this therapy is lifesaving, it is well known to impact vaccine- and infection-acquired immunity. The morbidity and mortality associated with infection is significant but education, early diagnosis and prevention through vaccination has the potential to improve outcomes. Assessing infection risk and longitudinal recovery of immune function post-ALL therapy are necessary to establish evidenced based therapeutic approaches.

### Objectives:

There are three main objectives to be accomplished by Aim 1 and Aim 2. Aim 1 will be to determine the overall infection incidence rate within the first year following completion of therapy for ALL, compared with the incidence of infection in matched healthy controls during the same time period. Aim 2 will describe seroprevalence for pneumococcus, varicella, and measles at approximately 3, 6, and 12 months following completion of therapy in patients with ALL and describe B and T lymphocyte subset recovery, specifically CD4+ T follicular helper cells (Tfh), using peripheral blood mononuclear cells (PBMCs) at about 3, 6, and 12 months following completion of ALL therapy

### Study Design:

This study will assemble a prospective, multicenter observational cohort of approximately 115 patients that are completing ALL chemotherapy at one of several pediatric hematology/oncology centers in the US (Children's Hospital of Philadelphia (CHOP), Lurie Children's Hospital of Chicago, Seattle Children's Hospital, Helen DeVos Children's Hospital, Children's Hospital at Vanderbilt, Christus Children's Hospital (Baylor College of Medicine), and Children's Hospital Los Angeles). Consented subjects will have a baseline enrollment visit followed by monthly check-ins via phone and/or chart review to determine if the enrolled patient had any documented viral or bacterial infections or symptoms (Aim 1) and 2) in-person visits at roughly 3, 6, and 12 months post-completion of ALL therapy to obtain blood samples to perform immune function studies (Aim 2).

For comparison of infection rates in patients post-ALL therapy to those of healthy control patients, once the follow-up period for the enrolled ALL cohort patients has ended, a cohort of matched healthy control patients will be assembled. Controls will be selected at a ratio of 3:1, with the full healthy control cohort including up to 330 total patients. The healthy control patients will be followed for the same one-year period as their matched ALL cohort patients. Control patients will be selected from patients who received care at CHOP beginning in 2022 and matched to ALL cohort patients based on age and sex.

### Setting/Participants:

---

This is a multicenter study at several pediatric hematology/oncology centers in the US (CHOP, Lurie Children's Hospital of Chicago, Seattle Children's Hospital, Helen DeVos Children's Hospital, Children's Hospital at Vanderbilt, Christus Children's Hospital (Baylor College of Medicine), and Children's Hospital Los Angeles). The study cohort will consist of up to 110 evaluable patients prospectively enrolled over the course of this study. Eligible patients include: Children, adolescents, and young adults diagnosed with B or T ALL at age 12 months or older; have completed up-front ALL therapy within the past three months or will complete ALL therapy in the upcoming three months, and are three years of age or older at time of enrollment. Patients who have a diagnosis of infant ALL, evidence of disease relapse, have a history of primary immunodeficiency (except related to Down Syndrome), received a stem cell transplant or cellular immunotherapy, or prior malignancy or condition requiring chemotherapy other than for current ALL diagnosis will be excluded.

All matched healthy control patients will be selected from the Children's Hospital of Philadelphia's Pediatric Research Consortium patient population regardless of where their matched ALL cohort patient was enrolled in the study.

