#### **3.2.2 Total Number of Study Sites/Total Number of Subjects Projected**

The study will be conducted at seven investigative sites in the United States. Other sites may be added in the future. It is expected that approximately 115 subjects will be enrolled over the course of this study to produce 110 evaluable subjects. Evaluable patients will be defined as patients that are enrolled and at least one blood specimen collected.

For each of the 110 enrolled evaluable subjects in the ALL cohort, at the end of the follow-up period, three age- and sex-matched healthy control patients will be selected for comparison, to assemble a cohort of 330 total healthy control patients. The full cohort,

---

including both ALL patients and 3:1 matched controls, is anticipated to include 440 evaluable patients.

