### 6.3 Statistical Methods

#### 6.3.1 Baseline Data

Baseline and demographic characteristics will be summarized by standard descriptive summaries. Categorical variables will be summarized by frequencies while continuous variables will be summarized by using mean, standard deviation, median, twenty-fifth and seventy-fifth percentiles, minimum and maximum.

#### 6.3.2 Analysis of Aim 1

Aim 1 (total number of unique infections identified within the first year after completing chemotherapy) will be reported as a rate per 1000 follow-up days. This rate will be reported for the entire cohort, by study site, and by demographics (e.g., age, race, gender). This outcome will also be reported within subsets of infection type (i.e., microbiologically documented infections and bacterial sinopulmonary infections) also reported as a rate per

---

1000 follow-up days for the entire cohort, by study site and by specific demographic variables. All infection rates will be reported as a post estimate with 95% confidence intervals. Patients will be censored at time of lost to follow-up or death.

Infection rates for enrolled patients will also be compared to those of controls matched on age and sex selected from the CHOP Pediatric Research Consortium (PeRC). Three healthy controls will be selected for each participant for a case to control ratio of 1:3. Control patient infection data will be obtained for the same follow-up time period as that of the matched case patient in order to match risk for infection from seasonal pathogens (e.g., if a case patient completed ALL therapy and enrolled in the study in January 2023, infection data for the matched controls would be collected from January 2023 through December 2023, the same follow-up period as that of the case patient). All control patients will be randomly selected, and control data will be collected when follow-up is complete for participants in the ALL cohort.

Infection rates will also be generated for patients who received blinatumomab as part of their chemotherapy regimen and those who did not receive blinatumomab.

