### **6.3.4 Control of Bias and Confounding**

For Aim 1, patients will be contacted once monthly for symptom reporting. Capture of the primary outcome will be dependent on completion of study visits, phone calls and complete data collection from the medical record. Accordingly, study procedural protocols will be implemented to ensure systematic approach for each enrolled subject. We will also develop a database that will inform a systematic approach to medical record review. This is a descriptive study and thus is not vulnerable to confounding.

To control for possible confounding in the comparison of infection incidence rates of ALL patients to those of healthy control patients, all healthy control patients will be matched to ALL cohort patients based on both age and sex, and controls will be assigned the same one-year “follow-up” period as those of their matched ALL cohort patients, to account for seasonal variation in infection rates as described above. Demographic data and vaccination histories

will be collected as outlined above for both ALL cohort patients and healthy controls to monitor for balance with respect to these important factors. Healthy control patients will be included only if they do not have pre-existing medical conditions that might put them at increased risk for infection to ensure assembly of a healthy cohort that most closely mirrors the general population of healthy children. Further, to reduce the risk of selection bias in the healthy control cohort, a waiver of consent and HIPAA authorization will be requested for these patients.

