Outcomes for Aim 2 are descriptive and thus power calculations are not provided. The point estimates for seroprevalence will inform if children retain protection against specific pathogens from vaccination administered prior to their diagnosis of and treatment for ALL. Point estimates for seroprevalence will be described for the entire cohort and by subsets of patient characteristics (e.g., chemotherapy inclusive of blinatumomab). The trajectory of recovery of B and T cell subsets will also be described for the sub-cohort of patients enrolled at CHOP. Differences in trajectories by patient specific characteristic (e.g., chemotherapy inclusive of blinatumomab) will also be explored. These granular descriptive immune function data will inform the need for revaccination in this patient population and if necessary, will provide guidance for the optimal design of revaccination studies.

---

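### All controls come from the CHOP network while ALL patients come from seven US centers, so for non-CHOP cases the Aim 1 rate ratio mixes disease with region

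*Combined protocol and SAP*

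**What the plan says.** - **Cases.** Section 3.2.2: "The study will be conducted at seven investigative sites in the United States". The Abstract lists them; CHOP is one, and others are in Chicago, Seattle and Los Angeles.
- **Controls.** The Abstract (Setting/Participants) takes every control from the CHOP consortium, "regardless of where their matched ALL cohort patient was enrolled in the study". Sections 3.2.1, 6.3.2 and 7.4 agree.
- **Matching.** Section 6.3.4: "all healthy control patients will be matched to ALL cohort patients based on both age and sex". Controls also receive the case's follow-up dates, which section 6.3.2 explains is done "in order to match risk for infection from seasonal pathogens". Site and region are not matching factors.
- **Analysis.** Section 6.3.2 reports ALL infection rates by study site, with 95% confidence intervals. It does not match on, stratify by or adjust for site when comparing cases with controls. Under section 6.3.4, demographics and vaccination history are collected "to monitor for balance with respect to these important factors"; no adjustment is specified.
- **Confounding.** Section 6.3.4 states: "This is a descriptive study and thus is not vulnerable to confounding". Its next paragraph then sets out how confounding in the control comparison will be limited. Geography is not mentioned.
- **CHOP share.** Not given. Section 6.4 describes the lymphocyte-subset work as being "for the sub-cohort of patients enrolled at CHOP", and sections 5.1.2.1.3 and 6.4 put that group at about 40 patients.

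**The concern.** The comparison with controls is part of the primary objective (section 2.1), and the power calculation in section 6.4 is built on its IRR. The endpoint counts infections documented at healthcare encounters, and the sinopulmonary subset also requires an antibiotic prescription (section 6.1). Local habits of attending, testing and prescribing therefore enter the rate directly, as does how heavy a given year was in a given region.

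In a matched set with a CHOP case, region is the same on both sides. In every other set, case and controls differ in region as well as disease, and the pooled IRR cannot separate the two. Section 6.4 also concedes that the healthy event rate is not accurately known, so the plan offers no benchmark against which a regional shift could be recognized.

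**Working it through.** **1. The plan's own figures.** Table 1 gives power of 80.1, 81.0, 80.1, 81.2 and 80.0% for 50 versus 150 patients at overdispersion φ = 1, 1.5, 2, 2.5 and 3. The formula is not named. A pooled-variance score test with variance φ × mean, simulated with 20,000 runs, gives 81.8, 81.0, 80.4, 79.9 and 78.0%, all within about 2 points. The point made here does not depend on a power error.

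**2. Effect of region on the IRR.** Let s be the share of cases outside CHOP and r the background recorded-infection rate at those sites relative to the CHOP network. With equal follow-up and the same true IRR everywhere:

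apparent IRR = true IRR × [(1 − s) + s × r]

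Both s and r are assumptions. If the 40 lymphocyte patients were all the CHOP cases, s = 70/110 = 0.64. A larger CHOP share makes s smaller.

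| s | r = 0.8 | r = 0.9 | r = 1.1 | r = 1.2 | r = 1.3 |
|---|---|---|---|---|---|
| 0.30 | 0.94 | 0.97 | 1.03 | 1.06 | 1.09 |
| 0.50 | 0.90 | 0.95 | 1.05 | 1.10 | 1.15 |
| 0.64 | 0.87 | 0.94 | 1.06 | 1.13 | 1.19 |

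At s = 70/110, the ends are 1 + 0.636 × (0.8 − 1) = 0.873 and 1 + 0.636 × (1.3 − 1) = 1.191. A true IRR of 1.45 would appear as 1.27 to 1.73, and a true IRR of 1.90 as 1.66 to 2.26.

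**3. Effect on the test.** Suppose the true IRR is 1, s = 70/110 and r is 0.8 or 1.2. Take Table 1's healthy rates (1.30 at φ = 1, 0.99 at φ = 3) and a two-sided 5% Wald test. For r = 0.8, φ = 1 and 110 versus 330:

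- ln(0.873) = −0.136
- SE = √[1/(110 × 1.30 × 0.873) + 1/(330 × 1.30)] = 0.102
- z = −1.34, so the rejection rate is about 27%

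| Patients | φ = 1 | φ = 3 |
|---|---|---|
| 110 vs 330 | 25–27% | 10% |
| 50 vs 150 | 14–15% | 7% |

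A larger sample makes this worse, because the bias stays fixed while the standard error shrinks.

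**4. Precision of a CHOP-only comparison.** The detectable IRR at 80% power solves

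ln(IRR) = (1.96 + 0.84) × √{φ × [1/(n × 1.88) + IRR/(3n × 1.88)]}

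where 1.88 per person-year is the ALL rate in section 6.4.

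| n cases vs 3n controls | φ = 1 | φ = 3 |
|---|---|---|
| 110 vs 330 | 1.26 | 1.51 |
| 40 vs 120 | 1.48 | 2.07 |

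For the effects in Table 1, Wald power is about 71–75% at 40 versus 120 and 84–87% at 55 versus 165.

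**5. Whether a CHOP versus non-CHOP interaction test would help.** Take 40 and 70 matched sets and an IRR of 1.45:

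SE = √{φ × [1/(40 × 1.88) + 1.45/(120 × 1.88) + 1/(70 × 1.88) + 1.45/(210 × 1.88)]} = 0.176 at φ = 1 and 0.305 at φ = 3

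Against r = 0.8 (|ln r| = 0.223) or r = 1.3 (0.262), power is about 24% or 32% at φ = 1, and 11% or 14% at φ = 3.

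**The case against.** **The single control source is a disclosed and practical choice.** One record system and one requested consent waiver serve all controls. The ALL-only infection rate and Aim 2 do not depend on it. This stands, but the comparison is still part of the primary objective.

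**The calendar match does more than it may seem.** A reader might infer that it fails because epidemics peak at different times in different cities. That goes too far. Case and controls share a window of about one year, so a peak some weeks earlier or later mostly stays inside it. What remains is yearly intensity and local care patterns.

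**Site is not ignored altogether.** A reader might infer that nothing in the report would hint at a regional effect. In fact, the CHOP ALL rate will appear in the by-site results, and all controls are CHOP patients. That is informal: it is not a matched contrast and has no planned IRR or interval.

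**The bias is assumed, not shown.** No regional rate is documented, and differences at the six other sites could partly cancel. A reader might also stretch the range to 0.84–1.24 by taking 80% of cases as non-CHOP. That would leave only 22 CHOP patients (0.2 × 110), which conflicts with a CHOP sub-cohort of about 40. The objection limits what can be said about size. It does not remove the structural mixing of region and disease.

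**Conclusion.** The concern holds in a limited form. For cases enrolled outside CHOP, the ALL-versus-control IRR is not controlled for region, and no planned analysis brings site into that comparison. If about 70 of 110 cases are non-CHOP and the background ratio is 0.8 to 1.3, the IRR is multiplied by about 0.87 to 1.19. For scale, the smallest detectable IRR at 110 versus 330 is 1.26 to 1.51. Both inputs are assumptions, and a larger CHOP share shrinks the effect. The documents do not support saying that the IRR is biased by a known amount or in a known direction. Matched sets with a CHOP case are free of this regional difference.

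**What to change.** 1. **Section 6.3.2:** add a pre-specified sensitivity analysis giving the matched IRR with 95% CI for CHOP-enrolled ALL patients against their own matched controls. Use the same method as for the all-site IRR, and report the two side by side whatever the result.
2. **Section 6.3.4:** state that the all-site IRR is not controlled for region, and withdraw, for this comparison, the statement that confounding cannot arise.
3. **Leave out** an interaction test and any rule that moves the conclusion to the CHOP sets if the two IRRs differ. With roughly 11–32% power, a nonsignificant test would reassure falsely. A switch would be data-dependent, and disagreement could also reflect real differences between the sites' ALL patients.

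**Cost.** Plan wording and one subset run; no new data. Section 6.3.2 collects control data only after ALL follow-up ends, so the analysis can be fixed in advance if that has not yet happened. The price is the lower precision shown in step 4.

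**What it will not cure.** Even within CHOP, ALL infections are also sought by monthly caregiver contact (section 6.3.4), while control infections come from an automated record pull with chart abstraction as needed (section 7.1). The CHOP-only IRR removes the regional difference but not this difference in ascertainment, and the report should say so.

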**Study Measures:**

Aim 1 will capture any infection documented at any inpatient or outpatient encounter documented by the managing medical team in the first year after completing ALL chemotherapy. An incident infection rate will be calculated for the cohort and compared with that of age- and sex-matched healthy controls during the same time period. The secondary aim will assess the seroprevalence for pneumococcus, varicella and measles among study subjects at approximately 3, 6, and 12 months after completion of therapy. This aim will also describe B and T lymphocyte subset recovery at these same timepoints. The outcomes for Aim 1 and Aim 2 will be described by certain demographic characteristics and underlying diagnoses, as well as ALL treatment protocol. Additionally, laboratory reports will be prospectively collected. These data will serve to define the infection rate in the first year after completing ALL chemotherapy and inform immune recovery overall and to specific vaccine preventable illnesses (i.e. varicella, measles, and pneumococcus).

**FIGURE 1: STUDY DIAGRAM****AIM 1: Incidence of overall infection**

Enrollment visit

- Monthly check-ins to capture data on inpatient and outpatient encounters
- In-person study visits at ~3, 6, and 12 months post-therapy
- Manual extraction from EHR: labs/microbiological data and therapeutic interventions

**REDCap**  
Research Electronic Data Capture

[figure not shown]

110 pediatric ALL patients at risk of infection

[figure not shown]
Outcome: Incidence of overall infection

**FIGURE 2: STUDY DIAGRAM**

Aim 2a: Seroprevalence for Pneumococcus, Varicella, and Measles  
Aim 2b: B and T lymphocyte subset recovery using PBMC

Enrollment visit

Evaluate at ~3, 6, and 12 months:  
Pneumococcal 23 serotype IgG,  
Varicella zoster virus IgG,  
Measles virus IgG,  
Total IgG,  
Peripheral blood mononuclear cells (PBMC)

**REDCap**  
Research Electronic Data Capture

Vaccine seroprevalence data for 110 pediatric ALL patients  
PBMC data for ~40 pediatric ALL patients

Outcome 2a: Seroprevalence status  
Outcome 2b: Timeline of immune recovery

---

## 1 BACKGROUND INFORMATION AND RATIONALE

### 1.1 Introduction

The treatment modalities of childhood cancer often have a significant impact on the immune system on survivors of childhood cancer. Although there is a robust body of literature that describes immunological outcomes, testing recommendations, and revaccination guidelines after allogeneic hematopoietic cell transplantation (HCT), immunological assessments are not routinely included in surveillance guidelines for survivors of childhood cancer that have not received HCT. As a result, survivorship care providers might not fully consider the impaired recovery of a child's immune system after cancer treatment if the child has not undergone HCT. Currently, survivors of childhood cancer who received standard therapy and missed scheduled vaccinations during their cancer therapy restart their vaccination schedule anywhere between 6 to 12 months after completion of treatment. For patients that completed a vaccine series, the Children's Oncology Group (COG) Hematopoietic Cell Transplant/ Immune/Dermatology Late Effects Taskforce recommends that providers and survivors consider either the use of boosters for previously administered vaccines, or the measurement of titers on which to base the administration of boosters. Despite these recommendations there are limited data on timing of immune reconstitution after ALL chemotherapy and effectiveness of the response to vaccines if administered. It is also acknowledged that there is a paucity of data on the frequency and outcome of infections among survivors in the first year after completion of therapy. Determining the frequency of infection in the first year post chemotherapy and documenting the recovery of immune function overall and to specific vaccine preventable pathogens will provide foundational data to guide current clinical decision-making and inform future clinical trials.

### 1.2 Relevant Literature and Data

Advancements in therapy have led to significant improvement in outcomes for children diagnosed with ALL, with overall survival rates now exceeding 90%. Although this therapy is lifesaving, its use is well known to impact vaccine- and infection-acquired immunity. As a result, infection remains a significant cause of morbidity and mortality during therapy. Published literature has documented that children with ALL have a 10-fold higher risk of invasive pneumococcal disease (IPD) during treatment for their cancer, with the highest risk occurring during maintenance chemotherapy. Importantly, this risk likely persists beyond the period of therapy receipt. The Childhood Cancer Survivor Study (CCSS) reported that survivors of all cancer were 1.6 to 2.7 times more likely to be hospitalized for infection >5 years following the completion of therapy compared with age-matched and sex-matched individuals in the general population. While these data are compelling there is a paucity of data documenting the frequency of infections or type of infections that occur in the first year following completion of therapy in children and adolescents with ALL. As such, clinicians do not have the necessary information to discuss infection risk with parents and their patients in this post-therapy period.

Additionally, there are limited data regarding the retention of seroprevalence for vaccine preventable infections during this post chemotherapy period. Significant interest exists in revaccinating children and adolescents after completion of therapy for ALL, however, the

---

necessity of such an intervention has not been clearly defined. Studies completed to date document that some children have low antibody titers to vaccine antigens immediately following treatment with therapy. However, these studies did not consider the possibility that patients further removed from their therapy will have more robust immune function recovery inclusive of vaccine antigen specific immune response. It is necessary to assess longitudinal recovery of immune function post-ALL therapy to better inform the need for revaccination among these children.

The proposed multicenter study will serve to define infection rates in the post-ALL therapy period in children, adolescents, and young adults and define the seroprevalence for vaccine specific antigens as well as presence of lymphocyte subsets at discrete time-points after therapy completion. These data will be immediately informative to clinicians aiming to manage expectations of parents for infection risk in their child post ALL therapy. Additionally, this prospective cohort represents an ideal opportunity to compare management decisions for children regarding timing of vaccination following completion of ALL therapy. Currently, The National Comprehensive Cancer Network (NCCN) recommend that survivors of childhood cancer who received standard (non- HCT) therapy and missed scheduled vaccinations during their cancer therapy should be given all vaccinations that were missed, beginning at 6 to 12 months after completion of treatment. Based upon lower-level evidence, the NCCN recommends that survivors of childhood cancer who were fully vaccinated before diagnosis, and who were treated with chemotherapy or radiotherapy (non- HCT), or both, engage with their provider in a shared decision making to determine approaches to revaccination that might be considered for the individual survivor.

One such approach might be to administer booster doses for all routine vaccinations without checking pre-vaccination titers. A different approach would be to measure antibody titers to determine levels of seroprotection first and then recommending booster doses if inadequate levels of seroprotection are found. Finally, in the absence of data for necessity to administer booster dosing, some centers may elect not to measure antibody titers or provider booster dosing. Not surprisingly, these options have led to variability in practice, even when centers have developed institution-specific guidelines. A survey of Canadian pediatric oncology centers found wide variation in the performance of post-treatment titers and reimmunization practices for survivors of ALL who have not had HCT. Data from this descriptive study will serve to inform future comparative trials designed to optimize vaccination protocols in the period after completion of ALL therapy.

At the end of 2024, the Children's Oncology Group reported data from a randomized controlled trial revealing improved effectiveness of ALL chemotherapy regimens inclusive of the novel biological agent blinatumomab. The improved outcomes of patients receiving ALL chemotherapy inclusive of blinatumomab has led to immediate transition to this regimen as standard of care for most patients with ALL. While blinatumomab may have improved effectiveness for cure of cancer it may alter immune reconstitution trajectories in the survivorship period. Because most of this study cohort was enrolled prior to the institution of blinatumomab as standard of care, it is uniquely positioned to now enroll ALL survivors that have or will have received blinatumomab as part of their chemotherapy

---

regimen. Including blinatumomab recipients will provide exploratory data on potential differences in immune reconstitution between patients receiving this new standard of care relative to prior standard of care ALL chemotherapy regimens.

